#### 2. Clinical measures

The difference between HCL insulin delivery vs standard therapy for the following measures

- i. Change in auxological parameters (height, weight)
- ii. Change in total daily dose, including basal and bolus proportion, carbohydrate ratios and insulin sensitivity

#### 3. Psychosocial:

- i. **Fear of hypoglycaemia**: Hypoglycaemic Fear Survey-II Worry scale: 17-<25years. Children's Hypoglycaemia Fear survey 12 – 17 years.
- ii. **Hypoglycaemia Awareness**: Hypoglycaemia Awareness Scale (Gold Score) (all ages)
- iii. **Anxiety**: State-Trait Anxiety Inventory (Child version for 12-15yrs, adult version  $\geq 16-\langle 25$ yr)
- iv. **Impact and Satisfaction**: The Diabetes Treatment Satisfaction Questionnaire status and change version (16 - <25years)
- v. **Quality of Life**: 12-<25 years: EO-5D-Y,
- vi. **Diabetes specific quality of life**: PedsQL Child version (12 yrs)Adolescent version (13 18yrs) and young adult version (18 <25yrs).
- vii. **Diabetes distress:** Problem Areas in Diabetes (Teen version for 12 17 years, standard version  $\ge 17 <25$ yrs)
- viii. Participant reported outcome for Automated Delivery system: INSPIRE Questionnaires: baseline and post-assessment versions Child version (12 year olds), Adolescent version (13-18) and adult version(18-25)

HCL outpatient Version Number: 6.0 Version Date: 15/07/2019

ix. **Semi structure interview** (all ages – post study, PCH only)

# 4. Human-technology interaction:

Describe participant technology interaction, adherence patterns and approaches that may improve it.

#### 5. Health-economic

Report the health economic impact of the MiniMed™ 670G Insulin Pump Hybrid Closed Loop System Vs standard therapy (MDI and CSII). The following data points will be used as part of the economic analysis:

- i. QALYs calculated from the EQ-5D
- ii. Hypoglycaemic events and HbA1c
- iii. Participant reporting on work interruption
- iv. Investigator reporting time spent on training, education and support, by the type of health professional resource used
- v. Diabetes management consumables (glucose strips, ketone strips, batteries, sensors, site dressings, lancets, needles, insulin).

#### 6. Biomarkers

Assess the difference between MiniMedTM 670G Insulin Pump Hybrid Closed Loop System vs standard therapy (MDI and CSII) after 26 weeks of treatment on the following biomarkers:

- i. Cell Adhesion Molecules (CAM)S
- ii. Soluble vascular cell adhesion molecules sVCAM
- iii. Soluble intercellular adhesion molecules sICAM
- iv. s-e Selectin
- v. Oxidized Low density lipoprotein
- vi. Myeloperoxidase.
- vii. MicroRNA signatures for arterial, renal and retinal complications
- viii. Telomerase
- ix. DNA methylation/acetylation
- x. Glycomark
- xi. Isoprostanes and proteomics
- xii. Clotting profile

#### 7. Performance Parameters

To report the performance of the MiniMed™ 670G Insulin Pump Hybrid Closed Loop System, and components. The following measures will be used:

[figure not shown]
- i. Proportion of time hybrid closed loop is active
- ii. Unplanned exits from closed loop (n)
- iii. Sensor performance mean absolute relative difference (MARD), sensor failures (*n*)

HCL outpatient Version Number: 6.0 Version Date: 15/07/2019

	iv. Insulin delivery line performance – reported delivery line							
	failures (n)							
	8. Health Care Providers Experiences							
	To report health care providers experiences and expectations of							
	hybrid closed loop systems through the study duration							
Baseline assessments	Visit 1:							
(SCREENING)	i) Auxological							
	a. Height							
	b. Weight							
	c. BMI							
	d. Date of Birth							
	e. Gender							
	ii) Diabetes clinical							
	

a. Date of diagnosis

b. Fasting C-peptide with paired glucose

							
	c. HbA1c							
	d. Seated blood pressure (average of 2 readings)							
	e. Total daily dose of insulin (mean of previous 7							
	days), basal and bolus proportion, carbohydrate							
	ratio and insulin sensitivity factor							
	ratio and insulin sensitivity factor  f. History of hypoglycaemic events in past 12 months							
(DANDOMICATION)								
(RANDOMISATION)	

g. History of diabetes ketoacidosis in past 12 months

h. Co-morbidities and medications

							
	iii) Psychology measures (baseline, age specific)							
	m, i sychology measures (baseline, age specific)							
	Visit 6:							
	i) CGM glycaemic data							
	

ii) Loss of work (participant/parent) or school

iii) Biomarkers

							
	·							
	iv) Total daily dose of insulin (mean of previous 7 days), basal and bolus proportion, carbohydrate ratio and							
	insulin sensitivity factor							
	insum sensitivity factor							
Midpoint assessments	Visit 11:							
	i) HbA1c ii) 2 weeks blinded CGM data, and all secondary glycaemic							
	ii) 2 weeks blinded CGM data, and all secondary glycaemic measures							
	iii) Treatment satisfaction							
	iv) Psychology measures							
	v) Total daily dose of insulin (mean of previous 7 days),							
	basal and bolus proportion, carbohydrate ratio and							
	insulin sensitivity factor							
	vi) Auxology (height, weight)							
	vii) Seated blood pressure (average of 2 readings)							
End of study assessments	Visit 16:							
	i) Auxological							
	a. Height							
	b. Weight							
	ii) CGM glycaemic data and all secondary glycaemic							
	measures							

	
 
iii) Seated blood pressure (average of 2 readings)
 
iv) Total daily dose, basal and bolus proportion, carbohydrate ratio and insulin sensitivity factor
 
v) Psychological assessments (age specific)
 
vi) Biomarkers
 
vii) Semi structured interview
 
						
Continuous Assessments	Technology interactions/human factors (repeated sampling)						
	through mobile phone app.  ii. Investigator time spent training (carbohydrate counting, HCL training) and support.  iii. Time off work and school  iv. Consumable use (sensors, pump sites)  v. Health care providers expectations and experiences (repeated sampling through mobile phone app)						
Procedures for safety	Safety measures will be recorded including ketone levels.						
monitoring during trial	Establishment of a data safety and monitoring board (DSMB) to scrutinise conduct of the study and study team and to monitor safety data arising from the study in order to determine if stopping the trial is required. Refer appendix 15.12						
Criteria for withdrawal of participants on safety grounds	A subject may terminate participation in the study at any time without necessarily giving a reason and without any personal disadvantage. An investigator can stop the participation of a subject after consideration of the benefit/risk ratio. Possible reasons are:  1. Serious Adverse Events 2. Inability to meet study requirements (e.g. regularly upload pump history to computer) 3. Technical grounds 4. Early termination of the study at the request of the steering committee or data safety monitoring board						

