#### 11.7 Subject withdrawal

A subject may terminate participation in the study at any time without necessarily giving a reason and without any personal disadvantage. An investigator can stop the participation of a subject after consideration of the benefit/risk ratio. Possible reasons are:

- 1. Serious adverse events
- 2. Non-compliance
- 3. Technical grounds (e.g. participant moves away)
- 4. Early termination of the study at the request of the steering committee or DSMB.

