# 15.11 Data Safety and Monitoring Board (DSMB): Terms of Reference

To safeguard the interests of the trial participants, monitor the main outcome measure including safety and efficacy, and monitor the overall conduct of the study. The DSMB should receive and review information on the progress and accruing data and provide advice on the conduct of the trial to the Investigators. The DSMB should inform the Lead Investigator if, in their view the results are likely to convince a broad range of clinicians, including those supporting the trial and the general clinical community, that, on balance, one trial arm is clearly indicated or contraindicated for all participants or a particular category of participants, and there was a reasonable expectation that this new evidence would materially influence participant management.

Interim review of the trial's progress including updated figures on recruitment, data quality, adherence to protocol, follow-up, and main outcomes and safety data. Specifically, these roles include to:

- 1. monitor evidence for differences in the main efficacy outcome measures
- 2. monitor evidence for harm
- 3. assess the impact and relevance of external evidence
- 4. decide whether to recommend that the trial continues to recruit participants or whether recruitment should be terminated either for everyone or for some treatment groups and/or some participant's subgroups
- 5. decide whether trial follow-up should be stopped earlier
- 6. assess data quality, including completeness (and by so doing encourage collection of high quality data)
- 7. maintain confidentiality of all trial information that is not in the public domain
- 8. monitor recruitment figures and losses to follow-up
- 9. monitor compliance with the protocol by participants and investigators
- 10. consider the ethical implications of any recommendations made by the DSMB
- 11. monitor planned sample size assumptions
- 12. suggest additional data analyses if necessary
- 13. advise on protocol modifications proposed by investigators or funders (e.g. to inclusion criteria, trial endpoints, or sample size)
- 14. monitor continuing appropriateness of participant information
- 15. monitor compliance with previous DSMB recommendations

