# Stopping Rules:

The DSMB will be responsible for the points above on a regular basis, and will report to the ethics committees and investigators if stopping the trial is required. Pre-defined stopping rules include:

In general, once a subject is randomized, he/she will remain in the study through the 26-week visit unless the investigator believes it is not safe for the subject to continue. However, the criteria below will be used to determine whether use of the HCL should be discontinued for a subject.

Rules for stopping bionic pancreas use for an individual subject are as follows:

- 1. Severe hypoglycemia
- 2. The participant withdraws consent for CHL use
- 3. Participant pregnancy

4. Noncompliance with the protocol or development of a new medical condition or need for chronic use of a medication which in the judgment of the investigator increases risk for the subject

If HCL use is stopped according to the above criteria, but the subject is willing, they will remain in the trial and will continue to make all of the scheduled visits and participate in all monitoring. The primary analysis will be intention to treat. Since subjects in the usual care arm are following their normal diabetes care regimen, there will be no change in their participation in the trial if they experience one of the events that would trigger stopping.

Study participation is voluntary, and subjects may withdraw at any time.

Criteria for Suspending/Stopping Overall Study

The DSMB will have the responsibility of determining if the overall study should be stopped. In case of a recurring system malfunction or participant safety issue observed with multiple subjects, the overall study will be suspended while the problem is diagnosed. The study may resume if the underlying problem can be corrected by a protocol or system modification that will not invalidate the results obtained prior to suspension.

An instance of severe hypoglycaemia in the HCL group will result in temporarily stopping additional enrolment of subjects until DSMB review of the data to determine whether the event was triggered by the system or not and whether it is safe to proceed.

The currently-enrolled subjects will continue use of the system during this time unless the DSMB determines it is unsafe for them to do so.

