The overall study will be stopped if the number of participants developing severe hypoglycaemia HCL group exceeds the number in the control Group by 5 or more at any time. However, the DSMB will have the authority to stop the study at any time because of safety concerns even if this criterion is not met.

The Coordinating Centre will track all participant withdrawals. If the above rule is met (HCL Group exceeding control Group by 5 or more), an emergency meeting of the DSMB will be convened within 7 days to review the data. In addition, the DSMB Chair may request a meeting at any time.

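### The withdrawal texts let an investigator end follow-up for non-compliance that is not unsafe, while the stopping rules by default keep randomised participants to week 26

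*Protocol*

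**What the plan says.** Three places in the protocol decide who stays in follow-up.

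- **Synopsis, row on withdrawal criteria.** The row is labelled as concerning safety. It gives the investigator discretion to stop a subject's participation after weighing benefit and risk. One possible reason is "Inability to meet study requirements (e.g. regularly upload pump history to computer").
- **Section 11.7, Subject withdrawal.** The same power is stated: "An investigator can stop the participation of a subject after consideration of the benefit/risk ratio". The possible reasons include bare non-compliance and "Technical grounds (e.g. participant moves away"). This section carries no safety label.
- **Appendix 15.11, Stopping Rules.** As a general rule, "once a subject is randomized, he/she will remain in the study through the 26-week visit unless the investigator believes it is not safe" to continue. A separate list gives grounds for stopping HCL use in an individual. It includes noncompliance, with a qualifier that the investigator judges the risk to the subject to be increased. The text continues: "If HCL use is stopped according to the above criteria, but the subject is willing, they will remain in the trial", attending every scheduled visit, and the primary analysis is by intention to treat. For the usual-care arm, "there will be no change in their participation in the trial if they experience one of the events that would trigger stopping".

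Neither withdrawal text refers to the stopping rules. The synopsis row just above the withdrawal criteria points to appendix 15.12 for the DSMB, but the DSMB terms and stopping rules are in 15.11.

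**The concern.** The first two texts end participation in the study. The third ends only use of the device and keeps the person in follow-up. For a participant whose non-compliance does not make further visits unsafe, a site could act on either, and nothing says which governs.

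This bears on the primary comparison because section 6.3.1 fixes the endpoint at weeks 23 to 26. A participant removed after one post-baseline visit but before week 23 belongs to the intention-to-treat set of section 7.3, yet has no sensor data from the endpoint window. The trial is open label, and the requirements that can be failed differ by arm. Removals for non-compliance could therefore be related to outcome and unequal between arms, which is the kind of loss that the retention rule in appendix 15.11 is meant to prevent.

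**Working it through.** **1. The same event under each text**

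| Event | Synopsis and section 11.7 | Appendix 15.11 |
|---|---|---|
| Non-compliance that makes continuing unsafe | Participation may be ended | Participation may be ended (safety exception) |
| Non-compliance that raises risk, but follow-up is safe | Participation may be ended | HCL use stops; a willing subject keeps all visits |
| Non-compliance that does not raise risk | Participation may be ended | No specific rule; the general default keeps the subject to week 26 |
| Control participant with a stopping event | Participation may be ended | Participation unchanged |
| Serious adverse event | Participation may be ended | Largely reconciled by the safety exception |

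The texts diverge in rows 2 to 4. Row 5 is not part of this point.

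**2. Whether missed uploads cost the primary data**

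Under 7.4 Visit schedule, the endpoint sensor data are downloaded when participants return to the clinic (visits 13 to 15), and visit 16 lists a 670G upload for HCL participants. Both are clinic visits, so pump data not uploaded at home can still be retrieved. A participant who fails to upload at home can provide the week 23 to 26 value if kept in follow-up.

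Upload duties differ by arm. HCL participants upload weekly in the start-up weeks (visit 7), pumps of CSII controls are uploaded at visit 8, and MDI controls have no pump.

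**3. Power**

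Inputs from section 7.2: difference 10 points, SD 13, two-sided 5%, 85% power, 64 per arm, 20% drop-out, 80 enrolled per arm. The same section also mentions an SD of 15.

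The plan's figure first: n per arm = 2 × (1.960 + 1.036)² × 13² / 10² = 30.3, so 31 (32 with the t distribution). The stated 64 per arm is not reproduced; it matches the total for both arms. That is a separate matter, but it explains the spare power here. The drop-out step does reproduce: 64 / 0.8 = 80.

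Power = Φ(10/SE − 1.96), with SE = SD × √(2/n):

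| SD | n per arm | SE | Power |
|---|---|---|---|
| 13 | 64 | 2.30 | 99.2% |
| 13 | 48 (40% loss from 80) | 2.65 | 96.5% |
| 15 | 64 | 2.65 | 96.5% |
| 15 | 48 | 3.06 | 90.4% |

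**4. Bias from unequal removal (illustration)**

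Let k be the net number removed from one arm of 80, and d the gap in mean time in range between those who stay and those removed. Neither is in the protocol; both are assumptions. The mean of those who stay differs from the mean of the whole arm by k × d / 80.

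For k = 5 and none in the other arm, SE = 13 × √(1/75 + 1/80) = 2.09.

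| d (points) | Shift per removal, d/80 | Shift for k = 5 | In SE units |
|---|---|---|---|
| 5 | 0.06 | 0.31 | 0.15 |
| 10 | 0.13 | 0.63 | 0.30 |
| 15 | 0.19 | 0.94 | 0.45 |

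Equal removals with equal d give zero. The sign reverses if removals fall mainly in the control arm.

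**The case against.** The strongest reply is that nothing here is a flat contradiction. The withdrawal texts are permissive and require benefit and risk to be considered, and the synopsis row is labelled as safety. The retention rule is itself stated as a general default, which leaves room for exceptions. The noncompliance item in appendix 15.11 carries a risk qualifier, so that appendix has no specific rule for non-compliance that does not raise risk.

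All of this stands, and it rules out two stronger readings. A reader might infer that the protocol orders the removal of anyone who misses uploads; it does not. A reader might also infer that two specific rules clash head on. For non-compliance without added risk, the clash is between an unlimited discretion and a default. It does not disappear, because section 11.7 has no safety limit, gives moving away as an example, and does not say that follow-up continues.

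It may also be said that uploads matter: the 670G upload is a listed source of glycaemic data for the HCL arm at visit 16, and early weekly uploads support the start of closed loop. That is correct, so it would go too far to call pump data irrelevant to the endpoint. The narrower claim holds: failing to upload at home need not lose those data.

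Finally, 20% drop-out is allowed for, "The Coordinating Centre will track all participant withdrawals", and the DSMB is to "monitor recruitment figures and losses to follow-up". These measures count losses. They neither recover a missing value nor tell a site which text to follow.

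**Conclusion.** The point holds as an unresolved inconsistency between a discretionary power to end follow-up and a default rule to keep it. Its consequence is avoidable loss of weeks 23 to 26 data that the protocol elsewhere intends to collect.

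The effect is probably small. Its size and direction cannot be estimated from the protocol, and the illustrative shift stays below half a standard error. A reader might infer that the primary result is seriously biased, or biased in favour of HCL. The protocol does not support either: it gives no removal counts or outcome gap, and it does not show that the differing upload duties would lead to unequal removals.

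The conclusion assumes that the endpoint is the week 23 to 26 measurement of the synopsis and section 6.3.1, although section 7.3 words it as an average during six months. How a missing value would be handled can be left to the SAP and is not criticised here. The case for change rests on conflicting instructions that are cheap to reconcile.

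**What to change.** In the synopsis row and in section 11.7:

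- State that non-compliance or missed uploads may stop use of the study device, but do not by themselves end follow-up in either arm.
- Cross-refer to the stopping rules in appendix 15.11, and correct the synopsis pointer to 15.12 at the same time.
- Keep four exits from follow-up: withdrawal of consent, the investigator's judgement that continuing is unsafe (including after a serious adverse event), practical inability to attend, such as moving away, and termination of the study by the steering committee or DSMB.
- Drop the pump-upload example, or limit it to stopping device use.

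Everyone else then keeps the scheduled visits and the week 23 to 26 CGM, as appendix 15.11 already plans by default. Recording reason and arm in the existing withdrawal tracking would help but is optional.

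The cost is wording in two places and a note to sites, with no visits beyond those scheduled. The one downside is that following non-compliant or off-device participants may slightly dilute the observed effect.

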# 2. Study flow

# 3. Introduction

There are over 120,000 people in Australia with Type 1 diabetes (T1D) (1). Approximately 10,000 of these are children and the incidence is increasing by around 3.5% each year (1). Despite modern treatment, complications of T1D and a reduced life expectancy continue to be a reality for patients. Attempts to aggressively manage blood glucose levels in order to avoid long-term complications are limited by difficulty, the risk of hypoglycaemia and the burden of care involved. Severe hypoglycaemia is associated with significant morbidity and even mortality and creates a fear of hypoglycaemia and anxiety for patients and their caregivers, affecting quality of life, and promoting behaviours aimed at avoiding hypoglycaemia (2). These actions lead to hyperglycaemia, placing patients at higher risk of developing long term complications. Fewer than a third of young patients in Australia reach a HbA1c of less than 7.5%, a target which has been shown to significantly reduce the development of complications associated with T1D (3, 4).

Approximately one third of patients with T1D have impaired hypoglycaemia awareness(5-8), and have an associated threefold increase in the likelihood of having a severe hypoglycaemic event(8). For the patient, repeated severe hypoglycaemic events have long lasting consequences which impact upon quality of life and daily activities such as driving. This results in increased anxiety and a greater burden on caregivers. The average cost of a severe hypoglycaemic event managed by the Australian health system is \$2430.65 (9), and this does not take into account costs incurred by the community due to time off work (caregivers and patients).

T1D diabetes affects cognitive function, social function, and places a large health and economic burden on families and the community(1). In 2008-2009, \$214 million of healthcare expenditure was for Type 1 diabetes (10). Patients with poor glycaemic control are likely to disproportionally contribute to healthcare costs. For all these reasons, it is essential to develop new therapies.

Almost universally, patients with T1D suffer from both hypoglycaemia and hyperglycaemia: this impacts their physical health, as well as their psychosocial wellbeing and places significant burden on communities including caregivers, families, workplace, and health service providers. The potential benefit of closed loop technology is to improve glycaemic control, while simultaneously reducing the burden of care for patients and carers, and improving psychosocial wellbeing. Hence, it is urgent that new innovations are made available to patients with T1D, and translated into routine clinical practice.

